#### 7.2.1.2 Pharmacokinetics

The pharmacokinetic parameters listed in Section  $\underline{2.1}$  and  $\underline{2.2.2}$  for EE and DRSP (components of COC Yasmin®) will be calculated according to the relevant BI internal procedures.

Plasma concentration data and parameters of a subject will be included in the statistical pharmacokinetic (PK) analyses if they are not flagged for exclusion due to a protocol deviation relevant to the evaluation of PK (to be decided no later than in the Report Planning Meeting) or due to PK non-evaluability (as revealed during data analysis, based on the criteria specified below). Exclusion of a subject's data will be documented in the CTR.

Important protocol deviations may be

- Incorrect trial medication taken, i.e. the subject received at least one dose of trial medication the subject was not assigned to
- Incorrect dose of trial medication taken
- Use of restricted medications

Plasma concentrations and/or parameters of a subject will be considered as non-evaluable, if for example

- The subject experienced emesis that occurred at or before two times median tmax of the respective treatment (Median tmax is to be determined excluding the subjects experiencing emesis),
- The subject experiences emesis at any time during the labelled dosing interval.
- Missing samples/concentration data at important phases of PK disposition curve

Plasma concentration data and parameters of a subject which are flagged for exclusion will be reported with its individual values but will not be included in the statistical analyses. Descriptive and inferential statistics of PK parameters will be based on the PKS.

Only concentration values within the validated concentration range and actual sampling times will be used for the calculation of pharmacokinetic parameters. Concentrations used in the pharmacokinetic calculations will be in the same format provided in the bioanalytical report, (that is, to the same number of decimal places provided in the bioanalytical report).

Proprietary confidential information © 2023 Boehringer Ingelheim International GmbH or one or more of its affiliated companies

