- 7. The intake of Yasmin® starts depending on the subjects' actual menstruation cycle and at least -28 days before Day 1 of first treatment period. In the run-in period, the subjects will take one tablet of COC daily until Day -8. On Day 7 to Day -1 no COC tablets will be given in order to induce withdrawal bleeding. Self-administration in the morning with no requirement of fasting. Self-administration to be documented in the diary. A negative urine pregnancy test should be performed at the site 1 to 7 days before start of the run-in. Details are outlined in Section 4.1.4
- 8. Urine pregnancy test. Additional urine drug screening on day 20 of each period.
- 9. Blood collection takes place within 10 minutes before dosing.
- 10. Suicidality assessment using the Columbia-Suicidal Severity Rating Scale (C-SSRS): 'Screening/Baseline' version at Visit 1, and 'since last visit' version at other visits.
- 11. Measurement of exploratory pharmacodynamic parameters: estradiol, luteinizing hormone (LH), follicle stimulating hormone (FSH), and progesterone. The samples will be taken in duplicate.
- 12. Dosing at the trial site after a continental breakfast (for details see Section 4.1.4).

c41232811-04 Trial Protocol

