## 1.2.2 Yasmin® (ethinylestradiol + drospirenone)

## 1.2.2.1 Ethinylestradiol

Ethinylestradiol (EE) is a synthetic estrogen with actions similar to those of estradiol. It is frequently used as the estrogenic component of combined oral contraceptives; a typical daily dose is 20 to 40 µg. Ethinylestradiol has also been used for hormone replacement therapy. Ethinylestradiol is also used for the treatment of female hypogonadism and the palliative treatment of prostate cancer and malignant breast cancer.

The adverse effects of EE and other estrogens are related, in part, to dose and duration of therapy, and to the sex and age of the recipient. In addition, adverse effects may be modified by administration of progestogen in combined oral contraceptives or hormone replacement therapy. Whether adverse effects of natural and synthetic estrogens differ, and whether the route of administration has an effect, is less clear. The use of estrogens in girls may cause premature closure of the epiphyses resulting in decreased final adult height. Large doses of estrogens used in palliative care have also been associated with nausea, fluid retention, venous and arterial thrombosis, and cholestatic jaundice. In men, large doses of estrogen cause impotence and feminising effects such as gynaecomastia. In women, uterine bleeding may occur after the cessation of estrogen therapy.

Ethinylestradiol is rapidly and well absorbed from the gastrointestinal tract with maximum plasma concentrations occurring after 1 h. The presence of an ethinyl group at the 17-position greatly reduces hepatic first-pass metabolism compared with estradiol, enabling the compound to be much more active after oral dosing, but there is some initial conjugation by the gut wall and systemic bioavailability is only about 45% (20-65%). Ethinylestradiol is highly protein bound (98%), but unlike naturally occurring estrogens which are mainly bound to sex-hormone binding globulin, it is principally bound to albumin. The apparent volume of distribution is 2.8 to 8.6 L/kg. It is metabolised in the liver by hydroxylation (mediated by CYP3A4) followed by glucuronidation (UGT1A1) and sulfatation of metabolites that undergo enterohepatic recycling. Metabolites are excreted via urine (40%) and bile (60%). The terminal half-life of ethinylestradiol is 10 to 20 h [R13-3708].

For a more detailed description of ethinylestradiol, please refer to the SmPC of Yasmin® [R23-0484].

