## 1.2.2.2 Drospirenone

Drospirenone (DRSP) is a synthetic progestin used in oral contraceptives for the prevention of pregnancy. It is commonly found in combination with EE in combined oral contraceptives (COC). Aside from its contraceptive effects, DRSP is used with estrogens to control acne and premenstrual dysphoric disorder. DRSP and EE in combination inhibit the release of follicle stimulating hormone (FSH) and luteinizing hormone (LH), resulting in ovulation suppression. Other changes include changes in the cervical mucus consistency, hindering sperm movement and preventing embryo implantation. DRSP is an analog of the diuretic spironolactone, which means that DRSP has ant mineralocorticoid activity. Therefore, DRSP should not be used in patients with renal or hepatic impairment or adrenal insufficiency. Progesterone and the progestogens may cause gastrointestinal disturbances, changes in appetite or weight, fluid

c41232811-04 Trial Protocol Page 18 of 84

Proprietary confidential information © 2023 Boehringer Ingelheim International GmbH or one or more of its affiliated companies

retention, oedema, acne, chloasma (melasma), allergic skin rashes, urticaria, mental depression, breast changes including discomfort or occasionally gynaecomastia, changes in libido, hair loss, hirsutism, fatigue, drowsiness or insomnia, fever, headache, premenstrual syndrome-like symptoms, and altered menstrual cycles or irregular menstrual bleeding. Anaphylaxis or anaphylactoid reactions may occur rarely (<0.01%).

After an oral dose DRSP is rapidly absorbed, with a bioavailability of about 76% due to first-pass effect. It is about 97% bound to plasma proteins, likely to albumin. The maximum concentration occurs within 1 to 2 hours. It is heavily metabolized with a terminal half-life of about 30 to 40 hours. DRSP undergoes oxidative metabolism via the hepatic cytochrome enzyme CYP3A4. The metabolites are excreted in urine and faeces. [R23-0688].

For a more detailed description of drospirenone, please refer to the SmPC of Yasmin® [R23-0484].

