## 2.1.3 Secondary endpoint

•  $C_{min,ss}$  (minimum measured concentration of the analyte in plasma at steady state over the uniform dosing interval  $\tau$ )

c41232811-04 Trial Protocol

Page 27 of 84

Proprietary confidential information © 2023 Boehringer Ingelheim International GmbH or one or more of its affiliated companies

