#### 6. INVESTIGATIONAL PLAN

#### 6.1 VISIT SCHEDULE

Exact times of measurements outside the permitted time windows will be documented. The acceptable time windows for screening and the end of trial examination are provided in the Flow Chart.

Study measurements and assessments scheduled to occur 'before' trial medication administration are to be performed and completed within a 2 h-period prior to the trial drug administration.

If not stated otherwise in the Flow Chart, the acceptable deviation from the scheduled time for vital signs, ECG, and laboratory tests will be  $\pm$  30 min.

If scheduled in the Flow Chart at the same time as a meal, blood sampling, vital signs, and 12-lead ECG recordings have to be done first. Furthermore, if several measurements including venipuncture are scheduled for the same time, venipuncture should be the last of the measurements due to its inconvenience to the subject and possible influence on physiological parameters.

For planned blood sampling times, refer to the Flow Chart. While these nominal times should be adhered to as closely as possible, the actual sampling times will be recorded and used for the determination of pharmacokinetic parameters.

During the run-in period, administration of Yasmin® tablets must be done by the subjects at home. The subjects are advised to take Yasmin® tablets with a cup of water at the same time each day, approximately between 06.00 and 10.00 am local time.

Ambulatory dosing in periods 1 and 2 should be performed between 06.00 and 10.00 am local time.

If a subject misses an ambulatory visit in weeks 1 or 2 of any period all efforts should be made for the subject to attend the visit as soon as possible. In such case dosing of Yasmin® can occur at any time of the day or can even be taken together with the next planned dose.

. If a subject misses 2 visits they must be separated by at least 7 days. Subjects who miss a visit in weeks 1 or 2 will be reminded of the importance of using additional contraception methods. All visits in week 3 must be attended. The relevance of measurements outside the permitted time windows will be assessed no later than at the Report Planning Meeting.

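### Do the emesis criteria for PK evaluability leave a harmful gap because they name no reference dose or analyte?

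*Protocol*

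**What the plan says.** Protocol section 7.2.1.2 (Pharmacokinetics) lists grounds for calling concentrations or parameters non-evaluable and introduces them as examples. Two concern vomiting:

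- "emesis that occurred at or before two times median" tmax of the respective treatment, with the median taken over subjects without emesis;
- "The subject experiences emesis at any time during the labelled dosing interval".

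The same section describes "PK non-evaluability (as revealed during data analysis, based on the criteria specified below"). It gives a second route to exclusion, a protocol deviation relevant to PK, which must be decided by the Report Planning Meeting. Every exclusion is to be documented in the trial report, and excluded values are still reported individually.

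The Flow Chart takes the full contraceptive profile only on Day 21 of each period, from pre-dose to 24 h. For the pre-dose sample, "Blood collection takes place within 10 minutes before dosing". Section 6.1 tolerates some missed visits in weeks 1 and 2 but says "All visits in week 3 must be attended". The secondary endpoint, Cmin,ss, is the "minimum measured concentration of the analyte in plasma at steady state over the uniform dosing interval" (section 2.1.3).

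The SAP has no emesis rule. It was written after the trial stopped in run-in and drops all PK analysis (SAP sections 4 and 7.4.1).

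**The concern.** Three things look wrong on a first reading.

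1. **Redundancy.** With once-daily dosing, a whole-interval window swallows one of twice tmax, so the tmax ground seems to do nothing.
2. **Missing reference.** No dose, day or analyte is named. There are 21 doses per period, and EE and DRSP are analysed separately with different tmax.
3. **A gap before Day 21.** Only Day 21 is fully sampled, so it is the natural reference. Emesis soon after the Day 20 dose, or Day 18 or 19, then falls outside both windows. Yet a dose vomited before absorption acts like a missed one, and the protocol insists on week 3 attendance.

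At stake is a Day 21 profile that is no longer at steady state. Cmin,ss would suffer most, because the Day 21 pre-dose sample would become the minimum. Non-evaluability is established during data analysis, so an unlisted case might be settled with concentrations in view in an open-label trial.

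**Working it through.** **Inputs.** EE: tmax about 1 h; "The terminal half-life of ethinylestradiol is 10 to 20 h" (section 1.2.2.1). DRSP: tmax 1-2 h; "It is heavily metabolized with a terminal half-life of about 30 to 40 hours" (section 1.2.2.2). Dosing interval 24 h. Planning case: 24 evaluable subjects, gCV 25%, two-sided 90% CI, 95% tolerance probability (section 7.5).

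**1. The plan's own figure.** The log-scale half-width is t(0.95, 23) x sqrt(2 s²/24), with s² = ln(1 + 0.25²) x chi²(0.95, 23)/23 = 0.06062 x 35.17/23 = 0.0927. This gives 1.714 x sqrt(2 x 0.0927/24) = 0.1506, and exp(0.1506) = 1.163. The protocol's 1.16 and its interval 86.02-116.26 reproduce. With 23 subjects the precision is 1.167, so one exclusion costs almost nothing.

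**2. Containment.** Twice tmax is 2 h (EE) or 2-4 h (DRSP), against 24 h. On the same dose, every case under the tmax ground is already a case under the interval ground. This would fail only if median tmax exceeded 12 h. The overlap therefore reclassifies nobody, and the choice between EE and DRSP tmax decides nothing.

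**3. One earlier dose lost in full.** By superposition, a dose given k days before Day 21 contributes q^k(1 - q) of the Day 21 AUC, with q = 0.5^(24/t½). For Day 20 and EE with t½ 20 h: q = 0.435 and 0.435 x 0.565 = 24.6%. Adding first-order absorption, with ka set to give the stated tmax, changes this by at most 0.3 points:

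| Dose lost | EE AUC (t½ 10 / 20 h) | DRSP AUC (t½ 30 / 40 h) |
|---|---|---|
| Day 20 | 15.6% / 24.8% | 24.6% / 22.5% |
| Day 19 | 3.0% / 10.8% | 14.1% / 14.9% |
| Day 18 | 0.6% / 4.7% | 8.1% / 9.8% |

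For Day 20 the fall in Cmin,ss is 1 - q: 81.1% / 56.5% (EE) and 42.6% / 34.0% (DRSP).

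**4. What emesis at a given time removes.** Only unabsorbed drug is lost, a fraction exp(-ka x t). The fitted ka is 4.2-5.0 per h (EE) and 2.3-5.8 per h (DRSP). Multiplying by the Day 20 losses above:

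| Emesis after the Day 20 dose | EE unabsorbed | EE AUC loss | EE Cmin,ss loss | DRSP unabsorbed | DRSP AUC loss |
|---|---|---|---|---|---|
| 30 min | 8-12% | about 2% | 4.6-10.1% | 5-31% | 1.2-7.7% |
| 60 min | 0.7-1.6% | about 0.2% | 0.4-1.3% | 0.3-9.7% | 0.1-2.4% |

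The large figures in step 3 therefore need vomiting essentially at dosing. Averaged over the window of twice tmax, only 9-12% of the dose is still unabsorbed.

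**5. Effect on the ratio.** One affected Test profile among 24 lowers the geometric mean ratio by 1 - (1 - L)^(1/24), where L is the fractional loss.

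- Full loss, AUC: 0.7% (L = 0.156) to 1.2% (L = 0.248).
- Full loss, Cmin,ss: 3.4-6.7% (EE), 1.7-2.3% (DRSP).
- Emesis at 30 min: AUC 0.08% (L = 0.02) to 0.33% (L = 0.077); EE Cmin,ss 0.2-0.4%.

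For EE Cmin,ss at gCV 25%, the CI widens by sqrt((0.1212 + d²/24)/0.1212), with 0.1212 = 2 ln(1 + 0.25²) and d = ln(1 - L). Full loss gives a factor of 1.11-1.40. At 30 min with L = 0.101, d = -0.106 and the factor is 1.002.

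**6. Frequency.** The documents give no emesis rate. Assuming 0.1-1% per subject-day, spread evenly over the day, 32 subjects x 2 periods x 3 days gives 0.19-1.92 events on Days 18-20. Of these, 0.02-0.32 fall within 2-4 h of dosing (x 2/24 to 4/24) and 0.004-0.04 within 30 min (x 0.5/24). Clustering after dosing would raise the last two figures.

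**The case for a change.** The strongest case for a change is that neither simple reading works well. On Day 21 alone, a vomited Day 20 dose is unlisted. Read on every dose, the interval ground would also discard a subject who vomited on Day 3, where the Day 21 AUC loss is at most 0.02%. A list of examples permits exclusion without specifying it, and evaluability feeds the replacement trigger in section 3.3.5. Vomiting is foreseeable, since section 1.2.2.3 lists it for Yasmin. Emesis onset times are already collected (section 5.2.6.2.1), so a fuller rule would need no new data.

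Much of this is true. No dose is named, and a Day 20 case would need judgement. But that judgement can rest on onset times recorded independently of the concentrations, and any exclusion has to be documented. PK work also follows internal procedures that are not public, and the SAP's silence reflects the early stop.

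A mechanical rule would not clearly do better. A cut-off at Days 18-20 has no basis in the contraceptive sampling; the Day 18-20 samples in the Flow Chart are for BI 1358894. It would keep a fully lost Day 17 DRSP dose, which costs 4.7-6.5% of AUC, and drop a Day 18 EE dose that may cost 0.6%. If its window used median steady-state tmax from Day 21, it could not be applied until concentrations were known, which is the very weakness it is meant to cure.

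**Conclusion.** No change follows. The overlap between the two grounds is harmless, and it makes the unnamed analyte harmless too. The unlisted Day 20 case is missing detail in an illustrative list, and the trial team can fill it sensibly under the plan as written.

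The effect on the primary comparison is at most 0.7-1.2% of the AUC ratio per affected subject in 24, and about 0.1-0.3% if emesis comes 30 minutes after dosing. Cmin,ss is more sensitive (EE up to 6.7%), but only when a dose is lost almost entirely. The stated precision of 1.16 is unaffected. Section 7.1 sets no acceptance range, so no pass/fail decision hangs on a shift of this size.

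These figures assume linear one-compartment kinetics, the protocol's half-lives and tmax, absorption starting at dosing, and loss of unabsorbed drug only. A lag after the breakfast would move the partial losses towards the full-loss bounds, which remain the upper limit. The emesis rates are assumptions. The SAP records that no subject started Period 1, so no result of this trial is touched.

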#### 7.2.2 Primary endpoint analyses

#### Primary analyses

The statistical model used for the analysis of the primary endpoints will be an analysis of variance (ANOVA) model on the logarithmic scale and will be applied to each analyte (EE, DRSP) separately. That is, the PK endpoints will be log-transformed (natural logarithm) prior to fitting the ANOVA model. This model will include effects accounting for the following sources of variation: subjects and treatment. The effects 'subjects' and 'treatment' will be considered as fixed. The model is described by the following equation:

 $y_{km} = \mu + \gamma_m + \tau_k + e_{km}$ , where

 $y_{km}$  = logarithm of response measured on subject m in receiving treatment k,

 $\mu$  = the overall mean,

 $\gamma_{\rm m}$  = the effect associated with the mth subject, m = 1, 2, ..., 32,

 $\tau_k$  = the kth treatment effect, k = 1, 2,

 $e_{km}$  = the random error associated with the  $m^{th}$  subject who received treatment k.

where  $e_{km} \sim N(0, \sigma_W^2)$  i.i.d. and  $e_{km}$  is an independent random variable.

Point estimates for the ratios of the geometric means (test/reference) for the primary endpoints (see Section 2.1) and their two-sided 90% confidence intervals (CIs) will be provided.

For each endpoint, the difference between the expected means for log(T)-log(R) will be estimated by the difference in the corresponding adjusted means (Least Squares Means). Additionally their two-sided 90% confidence intervals will be calculated based on the residual error from the ANOVA and quantiles from the t-distribution. These quantities will then be back-transformed to the original scale to provide the point estimate and 90% CIs for each endpoint.

#### Further exploratory analyses

The same statistical model as stated above will be repeated for the primary endpoints but the effect 'subjects' will be considered as random, whereas the effect 'treatment' will be considered as fixed."

[figure not shown]
In addition to the model based approach all parameters will be calculated and analysed descriptively.

#### 7.2.3 Secondary endpoint analyses

The secondary endpoint (refer to Section 2.1.3) will be calculated according to the relevant BI internal procedures and will be assessed statistically using the same methods as described for the primary endpoints.

19 Oct 2023

c41232811-04 Trial Protocol Page 60 of 84

### 7.2.5 Safety analyses

Safety will be analysed based on the assessments described in Section 2.2.2.3. All treated subjects (TS, refer to Section 7.2) will be included in the safety analysis. Safety analyses will be descriptive in nature and based on BI standards. No hypothesis testing is planned.

Boehringer Ingelheim BI Trial No.: 1402-0019

c41232811-04 Trial Protocol Page 61 of 84

19 Oct 2023

Proprietary confidential information © 2023 Boehringer Ingelheim International GmbH or one or more of its affiliated companies

For all analyses, the treatment actually administered (= treatment at onset) to the subject will be used (any deviations from the assigned treatment will be discussed in the minutes of the Report Planning Meeting).

Treatments will be compared in a descriptive way. Tabulations of frequencies/proportions will be used to evaluate categorical (qualitative) data, and tabulations of descriptive statistics will be used to analyse continuous (quantitative) data.

Measurements (such as ECG, vital signs, or laboratory parameters) or AEs will be assigned to treatments (see Section 4.1) based on the actual treatment at the time of the measurement or on the recorded time of AE onset (concept of treatment emergent AEs). Therefore, measurements performed or AEs recorded prior to first intake of trial medication will be assigned to the screening period. Those occurring in the run-in period will be assigned to the run-in period, while all others -from first trial medication intake in respective treatment period to end of REP (see Section 1.2.3) will be assigned to the respective treatment period. Events occurring after the REP but prior to end of study examination date will be assigned to follow-up'. In case of two or more treatments, the follow-up will be summarized according to the previous treatment. These assignments including the corresponding time intervals will be defined in detail in the TSAP. Note that AEs occurring after the last per protocol contact but entered before final database lock will be reported to Pharmacovigilance only and will not be captured in the trial database.

Additionally, further treatment intervals (analysing treatments) may be defined in the TSAP in order to provide summary statistics for time intervals, such as combined treatments, ontreatment totals, or periods without treatment effects (such as screening and follow-up intervals).

Adverse events will be coded using the Medical Dictionary for Regulatory Activities (MedDRA). Frequency, severity, and causal relationship of AEs will be tabulated by treatment, system organ class, and preferred term. SAEs, AESIs (see Section 5.2.6.1), and other significant AEs (according to ICH E3) will be listed separately.

Previous and concomitant therapies will be presented without consideration of time intervals and treatment periods.

Laboratory data will be compared to their reference ranges. Values outside the reference range will be highlighted in the listings. Additionally, differences from baseline will be evaluated.

Vital signs or other safety-relevant data will be assessed with regard to possible on-treatment changes from baseline.

In general, unless otherwise specified in the TSAP, the last non-missing measurement prior to first trial medication intake will be used as baseline for safety variables (laboratory data, ECG, vital signs).

Relevant ECG findings will be reported as AEs.

Results regarding the C-SSRS will only be listed.

